7.11. Vital Signs and Physical Examination Findings

At baseline, 3 orthostatic vital signs will be measured 10 min apart and the baseline score will be calculated as the average of 3 scores.

Observed and change from baseline in vital sign parameters (temperature, pulse/heart rate, respiratory rate, and blood pressure [standing and supine])) will be summarized by visit using descriptive statistics.

The number and percentage of subjects with any clinically important vital sign values during the study will also be summarized by visit. [Table 10](#) presents the criteria for the clinically important values.

Table 10: Clinically Important Vital Sign Values

Parameter	Age group (Years)	Low	High
Systolic Blood Pressure	2-5 yrs	<75	>110
	6-9 yrs	<80	>120
	≥10 yrs	<90	>130
Diastolic Blood Pressure	2-5 yrs	<35	>65
	6-9 yrs	<45	>75
	≥10 yrs	<50	>80
Heart Rate	1-2 yrs	<89	>151
	3-4 yrs	<73	>137
	5-7 yrs	<65	>133
	8-11 yrs	<62	>130
	≥12 yrs	<60	>119
Respiratory Rate	1-3 yrs	<22	>30
	4-6 yrs	<20	>24
	7-9 yrs	<18	>24
	10-14 yrs	<16	>22
	15-18 yrs	<14	>20
Temperature	All ages	< 35° C (95° F)	≥ 37.5° C (99.5° F)

The vital signs data will be listed. The subjects with any clinically important vital signs data will be listed in addition.

The number and percentage of subjects with abnormal physical examination will be listed and summarized by body system and visit.

7.12. Electrocardiogram

ECG at screening will not be listed.

7.13. Other Safety Parameters

Columbia-Suicide Severity Rating Scale (C-SSRS):

From the C-SSRS, the number and percentage of subjects reporting (1) at least one occurrence of suicidal ideation or behavior, (2) any type of suicidal behavior, and (3) any type of suicidal ideation during the study (from treatment start to 30 days after last dose or the end of treatment visit date, whichever is later) will be summarized.

Tanner Staging:

Observed and change from baseline in Tanner Staging will be listed and summarized by visit using descriptive statistics. Frequency distribution of tanner staging (1 thru 5) will also be summarized by visit.

8. PHARMACOKINETICS/PHARMACODYNAMICS

8.1. Pharmacokinetics

All concentrations below the lowest quantifiable concentration or missing data will be labeled as such in the concentration data presentation. Concentrations below the lowest quantifiable concentration will be treated as zero in the summary statistics. All subjects and samples excluded from the analysis will be clearly documented in the study report.

For each treatment group, descriptive statistics, including arithmetic mean, SD, coefficient of variation, geometric mean, median, minimum, and maximum will be calculated for the Topiramate or Levetiracetam plasma concentrations at each sampling time.

Topiramate and Levetiracetam plasma concentrations will be provided as listings.

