^b There may be an optional post-study follow-up phase to obtain DEXA measurements in a subgroup of subjects who experience a clinically important reduction (change in Z-score of -0.5 or greater) in BMD, based on local DEXA scan results, after 1 year of treatment with topiramate; these subjects will have a repeat DEXA scan 6 months after discontinuation of study drug.

^c The Day 1 visit will serve as the baseline visit. All procedures on Day 1 (except dispensing of study drug) should be completed before randomization.

^d The site will contact the subject via telephone at Month 13, to collect data on adverse events and concomitant medications.

^e Window for all visits will be ±7 days.

^f Adequacy of physical activity will be assessed with the Habitual Activity Estimation Scale.

^g Investigator will document inadequacy of any epilepsy treatment that the subject is receiving at the time of screening. Information regarding AED use and other medications within 2 years prior to the study will also be collected.

- ^h If possible, blood samples for determination of plasma topiramate and levetiracetam concentrations should be trough samples (taken immediately before the morning dose) and should coincide with samples drawn for clinical laboratory tests.
- ⁱ Subjects will be weighed in examination gowns or in lightweight clothing and without shoes. Height will be assessed using a wall-mounted stadiometer. All study site personnel measuring height will be blinded to treatment to avoid/minimize bias.
- ^j Orthostatic vital signs will be obtained for all subjects pending cooperation of subjects. A set of 3 measurements will be obtained at baseline only at intervals of 10 minutes. Thereafter, only 1 orthostatic vital sign measurement will be taken at all subsequent visits. The method for obtaining orthostatic vital signs will be as follows: subject will be supine for 5 minutes prior to measurement, and standing for 2 minutes prior to measurement.

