3. GENERAL ANALYSIS DEFINITIONS

Unless otherwise specified, all continuous endpoints (e.g., height, weight, BMD [observed and change from baseline values], etc.) will be summarized using descriptive statistics, which will include the number of subjects with a valid measurement (n), mean, SD, median, minimum, and maximum. Pharmacokinetics will be summarized using descriptive statistics including geometric mean and coefficient of variation (CV in percent will be defined as $CV(\%) = 100 * SD / \text{mean}$). All categorical endpoints (e.g., sex, adverse events, BMD Z-score decrease [>0.5 , >1.0 , >2.0], etc.) will be summarized using frequencies and percentages. In general, percentages will be calculated by dividing the number of subjects with the characteristic of interest by the number of subjects in the analysis population.

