3.3.4. Pharmacokinetics Analysis Set

The PK analysis set will consist of all subjects in the safety analysis set with available plasma concentrations.

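### The PK rule sets unquantifiable concentrations to zero and also requires a geometric mean, so one such sample makes that arm-and-visit geometric mean 0 or undefined

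*SAP*

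**What the plan says.** SAP 8.1 gives the handling rule without limiting it to particular statistics: "Concentrations below the lowest quantifiable concentration will be treated as zero in the summary statistics". Its next paragraph asks, for each treatment group, that "arithmetic mean, SD, coefficient of variation, geometric mean, median, minimum, and maximum will be calculated" for the "plasma concentrations at each sampling time". SAP section 3 repeats the requirement: "Pharmacokinetics will be summarized using descriptive statistics including geometric mean and coefficient of variation". Protocol 11.3 contains the same zero rule and the same list of statistics.

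Two other sentences might have supplied an exception. SAP 3.3.4 defines the population: "The PK analysis set will consist of all subjects in the safety analysis set with available plasma concentrations". That does not restrict the set to quantifiable values. SAP 8.1 also says: "All subjects and samples excluded from the analysis will be clearly documented in the study report". That requires exclusions to be reported, but it does not exclude unquantifiable samples from anything.

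The sampling times are Months 1, 3, 6 and 12 or early withdrawal (Protocol, Time and Events Schedule and section 3.1).

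**The concern.** Zero is a workable substitute for an arithmetic mean, a median or a minimum. It is not workable for a geometric mean, which is a product of the values, or equivalently the exponential of a mean of logarithms. The plan asks for both in adjoining paragraphs and does not say what to print when they collide.

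A programmer could defensibly produce different tables: a geometric mean of 0, a cell marked as not calculable, or a geometric mean over the quantifiable samples only. The last departs from the written rule and puts the geometric mean and the arithmetic mean of one row on different numbers of samples. The summary table is not required to show how many samples were unquantifiable, so a reader of that table alone could not be sure which of these had been done. What is at stake is the readability of one reported exposure statistic.

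**Working it through.** The plan states no figure to reproduce, so the check is on the formula and on its consequences under labelled assumptions.

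**Step 1: the formula.** GM = (x₁ × x₂ × … × xₙ)^(1/n) = exp[(ln x₁ + … + ln xₙ)/n]. If any xᵢ = 0, the product is 0 and GM = 0 for every n. In the log form, ln(0) is undefined. Depending on the software, the result is 0, an error, or a missing value that drops the sample from the mean of the logs.

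**Step 2: the arithmetic mean for comparison.** Adding one zero to n − 1 positive values multiplies the mean by (n − 1)/n. For n = 50 that factor is 49/50 = 0.98.

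**Step 3: size in simulated cells.** Assumptions: log-normal concentrations with median 8 and log-SD 0.5, one draw for each n, one unquantifiable sample, and 0.05 as an example of a positive substitute. None of these values is in the documents.

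| n | Mean, quantifiable only | Mean with the zero | GM, rule as written | GM, quantifiable only | GM, substitute 0.05 |
|---|---|---|---|---|---|
| 20 | 8.57 | 8.15 | 0 | 7.34 | 5.72 |
| 50 | 9.41 | 9.22 | 0 | 8.64 | 7.79 |
| 100 | 9.01 | 8.92 | 0 | 8.21 | 7.81 |

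The arithmetic mean barely moves, while the geometric mean is lost entirely.

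**Step 4: dependence on the substitute value.** Assume 29 quantifiable samples with geometric mean 5 mg/L and one sample below an assumed limit L, replaced by L/2. Then GM = 5 × exp[ln((L/2)/5)/30].

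- L = 0.1: 5 × exp[ln(0.01)/30] = 5 × exp(−0.1535) = 4.29
- L = 0.01: 5 × exp[ln(0.001)/30] = 5 × exp(−0.2303) = 3.97
- L = 1: 5 × exp[ln(0.1)/30] = 5 × exp(−0.0768) = 4.63

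The written rule gives 0 and the quantifiable samples alone give 5.0. A half-limit substitute gives 3.97 to 4.63 as the assumed limit varies tenfold either side of 0.1. The convention therefore has to be chosen in advance.

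**Step 5: how often a cell is affected.** The documents give neither a rate of unquantifiable samples nor the quantification limit. With assumed independent samples at rate p, P(at least one) = 1 − (1 − p)ⁿ:

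| n in cell | p = 1% | p = 2% | p = 5% |
|---|---|---|---|
| 20 | 18% | 33% | 64% |
| 50 | 39% | 64% | 92% |
| 100 | 63% | 87% | 99% |

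For example, 1 − 0.98⁵⁰ = 0.64. The sample-size section plans 100 completers per arm. The smaller cells are assumptions, but SAP section 1 records that enrolment was stopped early, and SAP 3.4 adds summaries by four age groups.

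**Step 6: whether such samples are plausible here.** Samples are to be troughs where possible. PK is also drawn at early withdrawal, and Protocol 10.2 asks for the end-of-study assessments when a child stops treatment. SAP Table 9 assigns samples by study day, with no on-treatment condition and an open-ended Month 12 window. A child already off drug could therefore contribute a value. This shows that the case can occur, not how often.

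**The case against.** The best defence is that little depends on this statistic. No PK parameters are estimated (Protocol 9.2.3), SAP 8.3 and 8.4 mark pharmacodynamics and PK/PD relationships as not applicable, and the CV is defined arithmetically in SAP section 3, so it survives. Unquantifiable values are to be labelled in the concentration presentation, all concentrations are listed, and exclusions must be documented. Under the zero rule a minimum of 0 on the same row would itself signal the problem. All of this stands, and it keeps the point small. It also means that dropping samples unannounced would breach the plan rather than follow it. None of it resolves the conflict for the geometric mean.

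Three stronger readings are tempting and are not supported:

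- A reader might infer that plasma level is the trial's only objective check of drug intake, because SAP 5.3 does not summarise compliance. But dispensed and returned drug is logged and inventoried at each visit (Protocol 7 and 14.5), a take-home record covers drug administration (Protocol 9.3), and SAP 5.4 summarises duration and daily dose and lists dispensed medication.
- A reader might infer that unquantifiable samples identify non-adherent children. The documents make no such link, and the value may come from a child who has already stopped treatment.
- A reader might infer that interpretation of the bone or growth results depends on this statistic. No analysis in SAP 7.2 to 7.4 uses concentration.

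**Conclusion.** The two instructions conflict as written, in both the SAP and the protocol. Any arm-by-visit cell with one unquantifiable sample has a geometric mean of 0, or an undefined one, regardless of the other values. This follows from the definition and needs no assumption. How many cells would be affected cannot be determined from the documents; the 39% to 92% for a cell of 50 rests on assumed rates of 1% to 5% and on independent samples.

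The consequence is limited to one descriptive statistic. The arithmetic mean, SD, CV, median, minimum and maximum remain usable, and no safety conclusion depends on the geometric mean. This is a minor correction, worth making because the written rule cannot give a meaningful answer where it applies and the repair is cheap.

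**What to change.** In SAP 8.1, keep zero for the arithmetic mean, SD, CV, median, minimum and maximum. Exempt the geometric mean from that rule and prespecify one convention for it. Any of these would do:

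- quantifiable values only, with their n shown;
- not calculated if any value in the cell is unquantifiable;
- half the lowest quantifiable concentration substituted. This makes the result depend on the assay limit and puts two substitutes on one row, so the limit should be stated.

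Print the number and percentage of unquantifiable samples per arm and visit on the summary table, so that the reader does not have to count them from the listing. State that the same exception applies to Protocol 11.3, so that the two documents agree.

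The cost is one sentence in the SAP, a matching note for the protocol, and a count with percentage on one table. Data collection does not change.

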8.2. Immune Response

NA

8.3. Pharmacodynamics

NA

8.4. Pharmacokinetic/Pharmacodynamic Relationships

NA

9. HEALTH ECONOMICS

NA

10. APPENDICES

Appendix 1: Cogstate Pediatric Normative Data**Table 1: CogState Pediatric Normative Data for the Detection Task.**

Age (years)	Males			Females		
	N	M	SD	N	M	SD
2	–	–	–	–	–	–
3	–	–	–	1	2.9041	–
4	2	2.8775	0.0534	3	2.8581	0.1732
5	4	2.7714	0.1001	10	2.7341	0.0871
6	5	2.6002	0.0717	11	2.8240	0.1660
7	6	2.6733	0.1357	9	2.7294	0.0622
8	4	2.6115	0.1769	6	2.8202	0.1598
9	4	2.5632	0.1146	3	2.5398	0.0714
10	1224	2.5631	0.0870	210	2.5882	0.0882
11	1499	2.5388	0.0826	506	2.5641	0.0899
12	1882	2.5290	0.0842	816	2.5447	0.0831
13	2322	2.5177	0.0851	1076	2.5255	0.0767
14	6551	2.5121	0.0853	3315	2.5252	0.0826
15	6399	2.5086	0.0810	3347	2.5213	0.0821

Note: The primary outcome variable for the Detection task is Reaction Time (Log10 transformation).

Table 2: CogState Pediatric Normative Data for the Identification Task.

Age (years)	Males			Females		
	N	M	SD	N	M	SD
2	–	–	–	–	–	–
3	–	–	–	1	3.1028	–
4	2	3.0312	0.0142	3	3.1244	0.0795
5	4	2.9061	0.0266	10	2.9546	0.1075
6	5	2.9199	0.0931	11	2.9938	0.1276
7	6	2.9238	0.1067	9	2.9310	0.0849
8	4	2.8885	0.1575	6	2.9726	0.1053
9	4	2.7421	0.0453	3	2.7632	0.0634
10	1198	2.7637	0.0759	203	2.7796	0.0735
11	1456	2.7323	0.0739	499	2.7453	0.0727
12	1823	2.7163	0.0712	811	2.7186	0.0726
13	2279	2.7007	0.0725	1073	2.6973	0.0711
14	6470	2.6889	0.0731	3300	2.6903	0.0719
15	6324	2.6809	0.0700	3335	2.6800	0.0717

Note: The primary outcome variable for the Identification task is Reaction Time (Log10 transformation).

Table 3: CogState Pediatric Normative Data for the One Card Learning Task.

Age (years)	Males			Females		
	N	M	SD	N	M	SD
6	5	1.0120	0.1845	11	1.0029	0.1441
7	6	0.9715	0.1175	9	0.9300	0.1616
8	4	1.1346	0.0765	6	0.9942	0.1889
9	4	1.0406	0.0376	3	0.9863	0.1306
10	1147	0.9639	0.0880	201	0.9636	0.0910
11	1449	0.9646	0.0889	485	0.9650	0.0892
12	1837	0.9719	0.0889	807	0.9692	0.0875
13	2249	0.9722	0.0858	1053	0.9767	0.0874
14	6435	0.9715	0.0870	3347	0.9679	0.0858
15	6559	0.9739	0.0868	3434	0.9718	0.0854

Note: The primary outcome variable for the One Card Learning task is Accuracy (arcsine square-root transformation).

Table 4: CogState Pediatric Normative Data for the One Back Task.

Age (years)	Males			Females		
	N	M	SD	N	M	SD
6	5	3.0924	0.0965	11	3.1386	0.1728
7	6	3.0799	0.0686	9	3.0789	0.0926
8	4	2.9574	0.0691	6	3.1290	0.1488
9	4	2.9524	0.0589	3	2.9646	0.1824
10	1278	2.9597	0.0984	218	2.9840	0.0990
11	1576	2.9225	0.0958	548	2.9405	0.0962
12	1973	2.8977	0.0962	879	2.9139	0.0972
13	2437	2.8824	0.0945	1130	2.8931	0.0938
14	7000	2.8673	0.0935	3604	2.8851	0.0930
15	7061	2.8547	0.0926	3663	2.8716	0.0952

Note: The primary outcome variable for the One Back task is Reaction Time (Log10 transformation).

Table 5: CogState Pediatric Normative Data for the Groton Maze Learning Test.

Age (years)	Males			Females		
	N	M	SD	N	M	SD
6	–	–	–	2	63.5000	16.2635
7	1	102.0000	–	–	–	–
8	–	–	–	1	68.0000	–
9	3	64.6667	24.0069	1	27.0000	–
10	20	73.8500	31.0251	6	67.3333	25.5943
11	14	67.6429	22.4828	12	64.1667	14.9595
12	20	62.9500	18.9667	6	61.0000	14.0855
13	10	53.2000	19.0660	11	65.0000	15.7861
14	5	61.6000	16.7422	2	46.0000	19.7990
15	–	–	–	1	39.0000	–

Note: The primary outcome variable for the Groton Maze Learning Test is Total Errors.

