Information regarding physical activity will be obtained at screening from the HAES (see [Attachment 1](#) for an example). Parents/caregivers will be asked how many hours their children spent in a 24-hour day in 1 of 4 categories of activity/inactivity to assess physical activity levels on the basis of the standardized and validated activity questionnaire. The total number of hours each subject spends in each category will be processed to determine the activity score on a scale of -100 (100% inactive) to +100 (100% active). A value of 0 indicates that the subject spent 12 hours of the day active and an equal number of hours inactive.²²

Renal Stone Evaluation

Renal ultrasounds (at screening, Month 6, and Month 12/early withdrawal; without sedation and after a 3-hour period during which only water, juice, or electrolyte solution will be permitted, as clinically indicated) will be performed under blinded conditions (after randomization) by a qualified radiologist or nephrologist at each site with age-appropriate inducers. The ultrasounds will be read/interpreted centrally (local reading at the screening visit is acceptable to determine eligibility for randomization; both the local and central readers will be blinded to the study treatment group). If possible, examinations should be done by the same individual at any given site.

Subjects with definite renal stones, nephrocalcinosis, or hydronephrosis at screening will be excluded from the study. Other abnormalities will be followed in subsequent examinations, which may occur more frequently at the discretion of the investigator in collaboration with the sponsor's medical monitor. Abnormalities will be reported to parents and primary-care physicians, and appropriate referrals will be made by the investigator if needed.

Cognitive, Developmental, and Behavioral Assessments

Cognitive, developmental, and behavioral assessments will be conducted as follows:

- Cogstate Battery (2 practice sessions, 1 at screening and 1 baseline prior to the baseline assessment; assessed at baseline, Month 6, and Month 12/early withdrawal):
 - ◊ For subjects 6 to 15 years of age, the Detection Test, Identification Test, One Card Learning Test, One Back Test, and Groton Maze Learning Test will be administered.
 - ◊ For cooperative subjects 4 to 5 years of age, the Detection Test and the Identification Test will be administered.

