- Language function test (Animal Fluency NEPSY-II (A Developmental NEuroPSYchological Assessment) Test - subjects 6 to 15 years of age; 1 practice session at screening; assessed at baseline, Month 6, and Month 12/early withdrawal)
- Vineland Adaptive Behavior Scale (to be completed by a parent or guardian for subjects 2 to 5 years of age, assessed at baseline, Month 3, Month 6, and Month 12/early withdrawal)

- Child Behavior Checklist (CBCL)-Parent version (Achenbach System of Empirically Based Assessment [ASEBA]) (assessed at baseline, Month 3, Month 6, and Month 12/early withdrawal)
 - ◊ Preschool version - subjects 2 to 5 years of age
 - ◊ School-age version - subjects 6 to 15 years of age

Note: For subjects who turn 6 years of age during the study, the Vineland Adaptive Behavior Scale, the preschool version of the CBCL, and only the Detection Test and Identification Test of the Cogstate Battery will continue to be administered throughout the study.

Cognitive Assessments

The Cogstate Computerized Test Battery^{15,26,30} requires less than 30 minutes to administer, and will be administered by non-expert (non-psychologist) study site personnel trained in the Cogstate administration method. All tests will be managed and scored centrally by Cogstate. The Battery includes tests that assess information processing speed and fine motor skills, attention, learning and memory, working memory, and executive functions. The tests were designed for multiple assessments over a short time period, with virtually no practice effects in adults and children. The pediatric version of the card tests (Detection Test, Identification Test, One Card Learning Test, and One Back Test) use cards with age-appropriate designs (ie, colors, shapes, and numbers) rather than using cards from a French playing card deck. However, the paradigms are the same.

- The Detection Test is a measure of information processing speed and fine motor skills, and uses a well-validated simple reaction time paradigm with card stimuli. In this test, the playing cards are all red and black. The subject is asked to press the Yes key as soon as the card in the center of the screen flips over.

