7. SAFETY

The safety variables to be summarized include kidney stones, height, weight, BMD and bone mineral content (BMC), biochemical markers of bone mineralization, bone age XR, seizure counts, cognitive, developmental, and behavioral assessments, treatment-emergent AEs, Columbia-Suicide Severity Rating Scale (C-SSRS), cognitive, developmental and behavioral assessments (COGSTATE computerized battery and NEPSY Language scale; Vineland Adaptive Behavioral Scale, Child Behavior Checklist (CBCL)), clinical laboratory tests (hematology, chemistry, urinalysis, and 24-hour urine collection), vital signs and physical exam. Safety variables are to be tabulated by descriptive statistics (n, mean, median, SD, minimum, and maximum; or n and percent). No formal statistical testing is planned.

For markedly abnormal labs and vital signs, age will be calculated at each visit to determine the criteria. Similarly, Vineland, CBCL and Cogstate will be calculated by age at each visit.

Z-scores for weight and height will be calculated using the SAS programs provided by the Centers for Disease Control (CDC) for the calculation of the 2000 CDC growth charts. Z-scores for the BMD and BMC will be provided by the central DEXA reading center (Bioclinica).

Z-scores for the DEXA scans will be calculated locally at baseline only to determine eligibility for the study, and centrally for all statistical analyses. The Z-score calculation will take the DEXA machine and the subject's age, sex, height, and ethnicity into consideration. The reference databases for calculating the Z-scores are provided in the DEXA Manual for this study (please see the imaging charter of attachment 1 for more details).

Longitudinal endpoints will be analyzed using a mixed-model repeated measures (MMRM) analysis. An MMRM analysis is included as sensitivity analysis to explore longitudinal safety data and will be analyzed in the following order.

1. The model includes treatment group, study center, age group (4 age groups), visit, treatment-by-visit interaction, baseline measure, and baseline-by-visit interaction with the unstructured covariance matrix.
2. If this model experiences convergence issues, then the same model with compound symmetric matrix followed by AR1 will be explored instead of unstructured.

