7.8. Cognitive, Developmental, and Behavioral Assessments

Cognitive Assessments

For the cognitive assessments (Detection Test, Identification Test, One Card Learning Test, One Back Test, and Groton Maze Learning Test) the standardized observed scores and change from baseline in standardized scores will be listed and summarized by visit using descriptive statistics. The standardized scores will be calculated by setting the observed raw score in relation to the expected within-subject standard deviations for each Cogstate task (see table 1-5 of [Appendix 1](#) for normative data). For the tasks which lower scores indicate improvement (e.g., Detection Test and Identification Test), the score will be multiplied by (-1), so that a negative change in standardized scores represent a decline in cognitive performance consistently across all tasks.

A meaningful decline in cognition has been defined as a change in standardized score of less than -1.65 from the baseline standardized score. These calculations will indicate meaningful decline at the subject level. Each individual change in standardized scores that meet the definition of a meaningful decline will be identified using a binary flag, where 1 represents a meaningful decline from baseline and 0 otherwise. The number and percentage of subjects with a meaningful decline in cognition will be listed and summarized by visit.

Cognitive assessments will be provided to subjects of 4 years and older. Cognitive data collected after a subject turn 16 will not be included in the analysis.

For example, if a 10-year-old female subject has an observed raw score at baseline of 1.2 for the detection test, then the standardized score will be $1.2/0.0882*(-1)=-13.605$. For a post baseline visit the subject had an observed raw score of 1.0, which is a standardized score of -11.338. The

change from baseline would be 2.267. The lower score at post baseline indicates an improvement in Detection Test which is reflected by the positive change (see table 1 of [Appendix 1](#)).

Developmental Assessments

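### Groton Maze scores cannot be standardised as planned: the norm table has no SD in 8 of 20 age-sex cells, no fallback is given, and a divisor that changes with age creates false change elsewhere

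*SAP*

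**What the plan says.** Protocol 9.3 sets who is tested: "For subjects 6 to 15 years of age, the Detection Test, Identification Test, One Card Learning Test, One Back Test, and Groton Maze Learning Test". Children who turn 6 during the study do not add to this group, because for them "only the Detection Test and Identification Test of the Cogstate Battery will continue to be administered throughout the study".

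SAP 7.8 sets the scoring: "The standardized scores will be calculated by setting the observed raw score in relation to the expected within-subject standard deviations for each Cogstate task", with Appendix 1 Tables 1 to 5 as the source. Table 5 is the one for this test, headed "CogState Pediatric Normative Data for the Groton Maze Learning Test". The worked example in SAP 7.8, a 10-year-old girl on the Detection Test, divides by 0.0882, which is the Table 1 SD for girls aged 10. SAP 7 adds: "Similarly, Vineland, CBCL and Cogstate will be calculated by age at each visit". SAP 5.1 defines that age as completed years at the visit date. The divisor is therefore specific to sex and to age at each visit.

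The subject-level outcome is also in SAP 7.8: "A meaningful decline in cognition has been defined as a change in standardized score of less than -1.65 from the baseline standardized score". The flag is 1 for a decline and 0 in every other case. Data collected after a child turns 16 are left out. SAP 3 says that percentages are in general taken over the analysis population.

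Protocol 11.4 describes a different order. The change from baseline is computed first and then scaled by a within-subject SD for each task.

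**The concern.** A score that needs a norm SD cannot be computed where the table has none. Table 5 is sparse, above all at ages 6 to 9, and the SAP names no substitute such as a pooled SD, a neighbouring age or another source. The planned change scores and decline percentages for this test would then be missing, or filled by a programmer's choice, for most of the younger school-age cells.

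Cognitive disorders are a listed event of interest for topiramate (protocol 11.4, SAP 7.9), so a decline table that quietly treats unscorable children as stable would mislead. There is a second problem. Raw scores are divided without first subtracting a norm mean, so any change in the divisor between visits shows up as change in the child.

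**Working it through.** **1. The plan's own figure.** Baseline: -1.2/0.0882 = -13.605. Post-baseline: -1.0/0.0882 = -11.338. Change: 2.267 from the rounded scores (2.268 unrounded). This reproduces the SAP 7.8 example and confirms the age- and sex-specific divisor.

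**2. Blank SDs in Table 5.** Ages 6 to 15 in two sexes make 20 cells.

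| Age | Boys: N, SD | Girls: N, SD |
|---|---|---|
| 6 | none | 2, 16.2635 |
| 7 | 1, blank | none |
| 8 | none | 1, blank |
| 9 | 3, 24.0069 | 1, blank |
| 10 | 20, 31.0251 | 6, 25.5943 |
| 11 | 14, 22.4828 | 12, 14.9595 |
| 12 | 20, 18.9667 | 6, 14.0855 |
| 13 | 10, 19.0660 | 11, 15.7861 |
| 14 | 5, 16.7422 | 2, 19.7990 |
| 15 | none | 1, blank |

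Eight cells have no SD: boys 6, 7, 8, 15 and girls 7, 8, 9, 15. Four have one norm child, for whom an SD is undefined, and four have none. The dashes are therefore real gaps and not a fault in reading the table.

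**3. Month 12 change.** This needs an SD at baseline age and at the age reached. Assuming birthdays spread evenly, (360 - 1)/365.25 = 98% of children are a year older at Day 360. With one birthday passed, both SDs exist for boys 9 to 13 (5 cells) and girls 10 to 13 (4 cells), so 9 of 20.

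- Baseline age 6 to 9: 1 of 8 cells computable (boys aged 9).
- Baseline age 10 to 12: 6 of 6.
- Baseline age 13 to 15: 2 of 6.
- Without the age-15 cells, whose Month 12 values mostly fall under the age-16 exclusion: 9 of 18, exactly half.

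Taking cells as equal and allowing for children with no birthday yet, the share not computable is 0.983 x 11/20 + 0.017 x 8/20 = 54.7% at Day 360. At Day 271, when the Month 12 window opens, it is 0.739 x 11/20 + 0.261 x 8/20 = 51.1%.

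**4. False change where both SDs exist.** Take an illustrative 65 errors at both visits, close to the Table 5 mean for girls aged 10 (67.3). For a girl going from 10 to 11: -65/14.9595 + 65/25.5943 = -4.35 + 2.54 = -1.81. That is below -1.65, so she is flagged with unchanged performance. The same happens for any unchanged score above 1.65/(1/14.9595 - 1/25.5943) = 59.4 errors.

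**5. A pooled Groton Maze SD.** Over the 12 cells with an SD, the sum of (N - 1) x SD^2 is 47,118 and the sum of (N - 1) is 99. The pooled SD is sqrt(47,118/99) = 21.8 errors. Only 3 of the 99 df come from children under 10 (boys aged 9: 2; girls aged 6: 1).

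**6. Would pooling suit the other tasks?** Tables 1 to 4 have an SD for every age and sex tested. Pooling Detection over ages 4 to 15 gives 0.083 on about 29,190 df, nearly all from ages 10 to 15. Ages 6 to 9 alone give 0.131 on 40 df. One all-age SD would inflate the youngest children's changes by 0.131/0.083 = about 1.6-fold.

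**The case against.** The strongest reply is about weight. Groton Maze is one of five Cogstate tests. Results are descriptive, with no formal testing (SAP 7). Cognition is neither a primary objective nor on the protocol's list of key safety endpoints. The other four tests can be scored in every cell, cognitive adverse events are tabulated separately, and continuous summaries report n, so missing scores would be visible there. All of this stands. It limits the importance of the point, but does not supply the missing rule.

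Some stronger readings are tempting, and the documents do not support them:

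- **That more than half of the children lose their Month 12 result.** The documents give no enrolled age-by-sex distribution, so only shares of cells can be stated. Even for cells, more than half depends on counting age 15; without those cells it is exactly half.
- **That young children are simply dropped from the decline percentage.** A flag of 0 in every case other than decline, with the general denominator in SAP 3, could instead keep them in as non-decliners. The SAP does not say which applies.
- **That the SD jumps from 14 to 31 between neighbouring cells.** Those values belong to girls aged 12 and boys aged 10. The largest drop between adjacent ages within a sex is 25.6 to 15.0 (girls 10 to 11).
- **That every Cogstate task should move to one all-age SD.** Step 6 shows the harm this would do at ages 6 to 9.

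**Conclusion.** The point holds as a fault in a secondary, descriptive safety measure that should be corrected. The stated scoring rule fails for 8 of 20 Groton Maze cells at any single visit. At Month 12 it yields a change in 9 of 20 cells (9 of 18 with age 15 set aside) and in 1 of 8 cells at baseline ages 6 to 9. The Month 12 counts rest on the SAP's age-at-visit rule and on one birthday having passed. If age were frozen at baseline, which the SAP does not say, the loss would be 8 of 20.

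The false-change problem is separate and also affects cells that can be scored. The 65-error score is illustrative, but the mechanism follows directly from dividing uncentred scores by different SDs.

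**What to change.** In SAP 7.8:

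- Follow protocol 11.4. Take the raw change first, then divide by one SD fixed per subject and task, with the same divisor at baseline and every later visit.
- For Groton Maze, use one SD for all ages and sexes: the vendor's within-subject SD if available, otherwise 21.8 errors (99 df, pooled from Table 5).
- For the other four tasks, do not pool across all ages. Use the SD for the child's baseline age and sex, or an age-band SD.
- Set the decline flag to missing when a score cannot be computed, take the percentage over subjects with computable scores, and report that number.

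The cost is SAP wording and reprogramming; no new data are needed. The downside should be stated with the results. The 21.8 is a spread between children and not a within-subject SD, and with 3 of 99 df from children under 10 it is an extrapolation for the youngest. With it, a flagged decline would need a rise of more than 1.65 x 21.8 = 36.0 errors.
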